Study Title: Operant H-reflex Down-conditioning of Rectus Femoris in Post-stroke Stiff Knee
Gait

NCT number: NCT05467774

Document Date: 7/28/2021

SUBJECTS

A total of 7 participants (5 unimpaired [H1-H5, ages 20-26 years, 3 M/ 2 F], 2 post-stroke [S1-S2, 1 M/1 F] were recruited for this study. Each participant was able to stand for 10-minute intervals unassisted, walk on a treadmill for 10-minutes, and provide informed consent. Exclusion criteria included: lower limb musculoskeletal injury (e.g., fractures, sprains, strains, tendonitis, or bursitis), functionally relevant weight-bearing restrictions, vision impairment and must not have taken antispasmodic medication one day prior to the session. All 7 people participated in down-conditioning. The study was approved by the University of Texas Institutional Review Board, and all subjects gave informed consent prior to participation. Both post-stroke individuals had right hemiparesis and the experiment was conducted on the right side.

ACQUISITION AND PROCEDURES

The experimental setup consisted of 8-channel surface electromyography (EMG) sensors (AMT-8, Bortec, Calgary, AL), bipolar electrodes (Ag-AgCl, Noraxon, Scottsdale, AZ) a constant current electrical stimulator (Digitimer DS8R, Hertfordshire, UK), a data acquisition board (NI-PCIe 6321, Austin, TX), a desktop computer, and EPOCS software (**Fig 1**). Additionally, during assessment sessions, stroke subjects walked on an instrumented split-belt force treadmill (Bertec, Columbus, OH), during which the ground reaction forces (GRF) were recorded at 1kHz, and lower limb kinematic data were recorded via inertial motion capture (IMU, Xsens, Enschede, Netherlands) at 60 Hz.

The experiment was conducted over 30 experimental sessions per individual, with 3 sessions per week on non-consecutive days. To prevent diurnal variation in H-reflex magnitude, all training

was performed at the same time of the day for each individual. Each experimental session consisted of preparation, femoral nerve navigation, recruitment and stimulation stages. The *preparation stage* started with drawing a grid on the surface of the femoral triangle on the leg. The femoral nerve was identified using an anatomical landmark-based method known as the “four-three finger technique”. Surface EMG electrodes were attached over the muscle belly of the rectus femoris (RF), medial hamstring (MH), vastus medialis (VM), and vastus lateralis (VL) based on commonly used anatomical landmarks^{31,32}. RF was the primary focus for H-reflex monitoring, MH was monitored for antagonist activity, and VM and VL were monitored to validate the training specificity of RF H-reflex conditioning. EMG activity was amplified, bandpass filtered (3-1,000 Hz), and sampled at 1 kHz.

[figure not shown]

Fig 1 Experimental setup and visual feedback of RF (rectus femoris) operant H-reflex conditioning. (a) Participant with electrodes on the right leg is in the upright standing posture, facing visual feedback from a computer monitor. **(b)** During control/baseline trials, only the

background EMG level of the RF was provided on the left bar graph. If the background EMG level of the RF and its antagonist pair MH (medial hamstrings) was within the shaded region, the bar remained green and the electrical stimulation was delivered. Otherwise, the bar turned red with no stimulation or trial progression. **(c)** During the training trial, RF H-reflex size and cumulative success rate were provided along with background EMG. The bar turned green if the RF H-reflex was below the threshold and turned red if larger than the threshold.

During the *femoral nerve navigation* stage, the optimal stimulation location of the femoral nerve was established via a monopolar probe electrode to each point on the grid drawn on the femoral triangle³⁴. Electrical stimulation was delivered as a square stimulus pulse, 1 ms in duration, intensity ranging between 10-20 mA or above depending on the individual, to elicit a reflex response with the subject in quiet standing. We monitored the time-course of the reflex response. The H-reflex was determined as the peak response following the initial stimulus artifact (<3 ms) and M-wave (~10-25 ms), typically within 30-40 ms post-stimulus. We used the following criteria to identify the optimal H-reflex response: 1) a clear biphasic shape, 2) a clear distinction from the M-wave or in case of contamination the biphasic signal lies on the downward slope of the M-wave, and 3) largest signal magnitude of all the candidate spots. After the optimal stimulation spot was located, the monopolar probe was replaced with a disposable Ag/AgCl snap electrode (circular, 1cm diameter) and the anode electrode (square 5x5cm) was placed over the surface of gluteus maximus on the ipsilateral side. To avoid session-to-session variability in electrode locations, the positions of all electrodes were marked using semi-permanent surgical skin marker. After electrodes were placed, a maximum voluntary contraction (MVC) for RF and MH were measured separately. Participants were asked to sit on a chair with their ankle fastened with a belt to the leg

of the chair and knee flexed to 90°. The investigator asked the participant to extend or flex their knee with maximum effort for 5-7 s. The participant repeated this three times with 15 s intervals in between. The representative MVC was determined as the mean of three MVC trials.

During the *recruitment stage*, the RF H-reflex recruitment curve was achieved with the subject in a quiet standing posture. Electrical stimulation was delivered at 0.14 Hz only if the background EMG level of RF and MH were within a 10-20% MVC window respectively, representing a slight tonic voluntary activation to avoid altering reflex excitability. To find the maximum M-wave amplitude of the RF, we increased stimulation intensity by 2 mA increments starting at 10 mA until the RF M-wave amplitude remained constant despite increasing current in three successive stimulus intensities, defined as M_{max} . For each stimulus intensity, two H-reflex responses were recorded. The H-reflex size was calculated as the mean of the peak-to-peak amplitudes of the two responses. The corresponding intensity (I_{max}) that elicited maximal representative H-reflex (H_{max}) was used in the following trials. Post-stroke individuals did not require any additional support for standing, however for safety purposes a handrail was placed in front of the individual.

During the *stimulation stage*, also in performed in a standing posture, the femoral nerve was stimulated at I_{max} at 0.14 Hz based on the same 10-20% MVC requirement. The first 6 sessions were baseline sessions with no feedback of RF H-reflex. Each baseline session was composed of 3 runs of 75 trials, where each trial was a single stimulation pulse. The next 24 sessions were training sessions. During training, each session began with 20 control trials with no feedback, followed by 3 runs of 75 trials using the peak-to-peak magnitude of RF H-reflex as visual feedback to the participant (**Fig 1**). During training sessions trials, M-wave size was monitored, and stimulus strength (I_{max}) was minimally adjusted to maintain the predetermined M-wave size. Post-stroke

individuals participated in an additional 2 assessment sessions, one before training and one after training sessions. In participant H4, in two of the 30 training sessions, the H-reflex showed overlap with the M-wave. In offline analysis, we used a best decaying exponential fit to obtain the H-reflex estimate as illustrated in our earlier work.

FEEDBACK

As shown in **Fig 1c**, visual feedback consisted of 1) RF and MH background EMG (left bar), 2) RF H-reflex (right bar), 3) trial number, and 4) cumulative success rate. The left bar was green if the background EMG was below activation threshold but was red otherwise. The H-reflex stimulation was delivered only when the background EMG bar was green. The participant was provided with the objective to reduce the height of the right bar, representing H-reflex amplitude, below a given threshold (shaded area in **Fig 1c**). The threshold was updated for each run as the 66th percentile of the H-reflex trials from the previous run. If below the performance threshold, the right bar turned green and cumulative success rate was adjusted accordingly. If above the threshold, the bar turned red, and the success rate fell. Each trial was 7 s duration, with a single stimulation pulse stimulation of 1 ms pulse width followed by feedback for the remainder of the trial. Each session was recorded on a different non-consecutive day, up to 3 times per week. The 6 baseline sessions each consisted of 3 runs of 75 control trials (225 total), while each of 24 training sessions consisted of 20 control trials and 3 runs of 75 training trials (245 total) in standing posture. Subjects were exposed to H-reflex feedback only during the training trials, and no H-reflex feedback was given during the control trials. The participant's score for each run was cumulative success rate ($Scr = \frac{N_{success}}{N_{trial}} \%$) and participants were rewarded in proportion to one's score (i.e., $Reward(\$) = 1.0 + 0.05 * (Scr - 50)$). If the participant was successful in achieving three

consecutive success rates that were equal to or higher than 90% for all three runs, they were provided with an extra dollar as bonus, which made the maximum additional compensation amount \$10.00. A rest period was provided between each run to minimize fatigue, which could affect muscular responses to stimuli.

CLINICAL ASSESSMENTS

The two individuals with stroke participated in pre and post training assessment sessions. Participants performed a 10 m walk test (10MWT) with instructions to walk with maximum effort. This process was repeated 4 times and the participant's gait kinematics were recorded using inertial motion capture. Next, participants completed the quadriceps pendulum test, which is a non-invasive biomechanical method of evaluating spasticity using gravity to provoke muscle stretch reflexes during passive swinging of the lower limb. Inertial measurement units were attached on top of thigh, shank, and foot to calculate the knee joint angle during the process. This test was repeated 3 times with 30 second rest periods in between. The main outcome of this test was quadriceps reflex threshold angle (QRTA), which was the angle difference from the maximum knee extension position to the first swing excursion, the first transition period of knee flexion to knee extension. Lastly, the participant was asked to walk on an instrumented treadmill while their gait kinematics, ground reaction forces (GRF), and H-reflexes were obtained. During treadmill walking, four gait phases (heel-strike, toe-off, mid-stance, and mid-swing) were detected in real-time using online GRF data using conventional gait analysis¹. Heel-strike was detected when GRF value exceeded a predetermined force threshold (F_{th}) for the first time (0% gait cycle) and toe-off was detected with GRF dropping below the threshold (F_{th}) (60% gait cycle). Mid-stance was detected as the time point when 30% of step duration, pre-calculated from one's step length and gait speed, had elapsed from the moment of heel-strike. Mid-swing was determined in a similar

manner, which was detected at the 80% gait cycle. The H-reflex was elicited and measured only when a desired gait phase was detected and occurred at least 7 s after the last H-reflex trial. Twenty H-reflexes were recorded for each gait phase. A 5 min break after each of four runs was provided to minimize the effect of fatigue on H-reflex. The main outcomes consisted of 1) knee flexion range of motion (RoM), 2) peak knee flexion velocity, and 3) H-reflex amplitude during the four different gait phases.

OUTCOME MEASURES

We normalized the H-reflex measurements. For each session, the H-reflex was normalized with the session's maximum motor response (M-wave, M_{max}), which is the most commonly used method of normalization⁴⁰. To directly compare between session-to-session performances, each session's H-reflex trial was averaged, normalized by M_{max} , and represented as a percentage (%) of the mean H-reflex of 6 baseline sessions. Main outcome measures of each session were the average of 225 peak-to-peak H-reflex responses from the RF and VM.

STATISTICAL ANALYSIS

We investigated the hypothesis that RF H-reflex can be down-conditioned through operant H-reflex conditioning. We first verified normality of the data using a Shapiro-Wilk test. To validate the effect of training, a paired t-test ($\alpha < 0.05$) was used to compare the mean of the 225 normalized H-reflex trials during 6 baseline sessions to that of the last 6 training sessions.

ETHICS APPROVAL

This study was conducted according to the Declaration of Helsinki and had ethical approval from the University of Texas Institutional Review Board. All subjects gave written informed consent prior to data collection.

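### VM and VL are recorded to show that conditioning is specific to RF, but no RF-versus-VM or RF-versus-VL contrast is planned

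*Combined protocol and SAP*

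**What the plan says.** In the combined protocol and SAP, the preparation stage under Acquisition and Procedures gives the purpose of the extra quadriceps channels: "VM and VL were monitored to validate the training specificity of RF H-reflex conditioning". Under Outcome Measures, "Main outcome measures of each session were the average of 225 peak-to-peak H-reflex responses from the RF and VM". VL is not named there.

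Statistical Analysis states one hypothesis: "We investigated the hypothesis that RF H-reflex can be down-conditioned through operant H-reflex conditioning". It states one test, a paired t-test at 0.05 that "was used to compare the mean of the 225 normalized H-reflex trials during 6 baseline sessions to that of the last 6 training sessions". That sentence names no muscle. No between-muscle contrast, muscle-by-time interaction or decision rule for specificity appears anywhere.

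All seven participants were trained, so there is no control group. The recruitment stage describes the search for the maximal motor response for one muscle only ("To find the maximum M-wave amplitude of the RF"). Outcome Measures divides each session's H-reflex by that session's Mmax and expresses the result as a percentage of the mean of the six baseline sessions.

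**The concern.** Specificity is a statement about a difference between muscles: RF fell more than VM or VL did. A within-muscle test cannot support it. If only RF is tested, the stated purpose of recording VM and VL has no analysis. If VM is tested in the same way, the remaining route is to set a significant RF result beside a non-significant VM result. That does not test a difference, and with seven people a non-significant VM result says little.

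The same gap affects attribution. In one trained group, a fall from baseline to the last six sessions could reflect conditioning, or a general decline in quadriceps reflexes over 30 sessions of repeated stimulation. VM and VL are concurrent, untargeted comparators that could remove the part of such a decline that RF shares with them. No planned test uses them in that way.

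**Working it through.** **The plan's own figures.** No effect size, SD, correlation, power or sample-size calculation is given, so there is no figure to reproduce. The counts agree: 3 × 75 = 225 trials per baseline session, 20 + 225 = 245 per training session, 6 + 24 = 30 sessions.

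**Inputs.** From the document: n = 7, paired t-test, level 0.05. Assumed: two-sided test; participant as the unit; true drop of 10 to 20 percentage points; between-person SD of the change 10 to 20 points; RF–VM correlation of changes (ρ) 0 to 0.8. Write d = drop/SD.

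**Step 1: power of one within-muscle test.** Power = P(|T| > 2.447), where T is noncentral t with 6 df and noncentrality d√7.

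| d | Power |
|---|---|
| 0.5 | 0.20 |
| 1.0 | 0.60 |
| 1.5 | 0.91 |
| 2.0 | 0.99 |

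80% power needs d = 1.27. A true VM change of d = 0.5 would be missed about 80% of the time.

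**Step 2: RF significant, VM not, when both change equally.** At ρ = 0 the rate is power × (1 − power). For d = 1 this is 0.60 × 0.40 = 0.24. The other values come from simulation (100,000 runs per setting).

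| Drop, SD (points) | ρ = 0 | ρ = 0.3 | ρ = 0.6 | ρ = 0.8 |
|---|---|---|---|---|
| 15, 15 | 24% | 20% | 16% | 11% |
| 15, 10 | 8% | 8% | 6% | 5% |
| 20, 10 | 0.9% | 0.9% | 0.7% | 0.6% |

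At drop 15 and SD 15, among trials with a significant RF result, 40% (ρ = 0) to 26% (ρ = 0.6) would look RF-specific although they are not. The direct paired test of RF change minus VM change rejects in about 5% of trials in every setting.

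The document does not say whether the t-test's unit is the participant or the session. With six session pairs as the unit, and d from 0 to 1.5, the rate is 3% to 25% for ρ from 0 to 0.8.

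**Step 3: drift alone.** With no training effect, a common drift of d = 0.25, 0.5, 1.0 or 1.5 gives p < 0.05 in 9%, 20%, 60% or 91% of studies at n = 7, against a nominal 5%.

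**Step 4: power of the direct contrast.** With equal SDs, its standardised effect is (d for RF − d for VM)/√(2(1 − ρ)). For RF d = 1 and VM unchanged:

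- ρ = 0: 1/1.414 = 0.71, power 35%
- ρ = 0.3: 1/1.183 = 0.85, power 47%
- ρ = 0.6: 1/0.894 = 1.12, power about 70%

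If VM changes half as much as RF, power is 12%, 16% and 24%.

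**Step 5: which trials are compared.** Baseline trials carry no H-reflex feedback. The 225 trials of a training session match its three feedback runs. The 20 no-feedback control trials that open each training session are the like-for-like comparison with baseline, and no analysis of them is stated.

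**The case against.** Several stronger readings are tempting, and the document does not support them.

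- *Only RF is tested.* A reader might infer this from the hypothesis, which concerns RF alone. But the test sentence names no muscle and VM is a main outcome, so VM may get the same test. VL is the muscle with neither an outcome nor a test.
- *The plan commits to an invalid specificity conclusion.* It does not. It states no specificity rule and never says that two p-values will be compared. The defect is a stated purpose with no matching analysis.
- *VM is put on the wrong scale.* How VM is normalised is not stated. If RF's Mmax were used, a constant scale difference would cancel in percent of baseline. In a log contrast between muscles a shared Mmax would largely cancel too. What remains is session-to-session change in each muscle's own recording, which a shared divisor does not correct.
- *Drift is uncontrolled.* The plan fixes the time of day, marks electrode positions, holds M-wave size during training and normalises to Mmax each session. These act directly on electrode and stimulus drift. They do not identify habituation or a general time effect.

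Two further objections stand. The 24% rate is close to the 25% ceiling of p(1 − p), and it falls when the muscles are strongly correlated or the effect is large. VM is also an imperfect control: it has its own electrodes, and the stimulus intensity is chosen from RF's recruitment curve.

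**Conclusion.** The concern holds as a gap in a secondary aim that should be closed. The RF hypothesis can still be tested as written, but the specificity aim cannot be met by any within-muscle test. Reading specificity from separate tests would mislead in under 1% to 24% of trials when the true changes are equal, against 5% for the direct contrast. That range rests entirely on assumed drops, SDs and correlations, and on n = 7 participants as the unit. The limit on attribution follows from the single-group design and does not depend on those assumptions; how large any drift would be is unknown.

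**What to change.** 1. Add a participant-level paired contrast: log(last-six mean/baseline mean) for RF minus the same quantity for VM, and likewise for VL, each with a 95% confidence interval. If VL is to be left out, give the reason.
2. Base any specificity statement on that interval. Treat an interval that includes zero as inconclusive, not as evidence that the effect is not specific.
3. Normalise VM and VL to their own Mmax where the RF stimulus ramp reaches their plateau, and say what is done where it does not.
4. Repeat the RF test and the contrast on the 20 no-feedback control trials of the last six training sessions.
5. State the unit of the t-test and which muscles it covers.

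The cost is SAP wording and a few lines of code on EMG already recorded. Because the document is written in the past tense, label the contrast as added afterwards if the results have been seen.

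Downsides to state: power is only about 35% to 70% in the favourable case above (RF d = 1, VM unchanged, ρ = 0 to 0.6). Spill-over of learning to VM shrinks the contrast. It removes only drift common to both muscles. The control-trial means are noisier: 6 × 20 = 120 trials against 6 × 225 = 1,350.

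### Does sampling EMG at 1 kHz behind a filter that passes up to 1,000 Hz undermine the H-reflex outcome?

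*Combined protocol and SAP*

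**What the plan says.** The preparation stage under ACQUISITION AND PROCEDURES gives the EMG settings: "EMG activity was amplified, bandpass filtered (3-1,000 Hz), and sampled at 1 kHz". No other EMG rate, anti-alias filter or interpolation step is described. The same 1 kHz figure appears in the equipment paragraph for a different signal: "the ground reaction forces (GRF) were recorded at 1kHz".

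The amplitudes used in the analysis come from this record.

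- **H-reflex.** OUTCOME MEASURES states: "Main outcome measures of each session were the average of 225 peak-to-peak H-reflex responses from the RF and VM". Each session's value is divided by that session's M_max and "represented as a percentage (%) of the mean H-reflex of 6 baseline sessions".
- **M_max.** In the recruitment stage current is raised "until the RF M-wave amplitude remained constant despite increasing current in three successive stimulus intensities", and "For each stimulus intensity, two H-reflex responses were recorded".
- **Consistency between sessions.** "To avoid session-to-session variability in electrode locations, the positions of all electrodes were marked using semi-permanent surgical skin marker".

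STATISTICAL ANALYSIS then compares the six baseline sessions with the last six training sessions by a paired t-test.

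**The concern.** Two separate things look wrong.

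First, a signal sampled at 1 kHz can carry frequencies only up to 500 Hz, while the stated filter passes content up to twice that. Any background EMG or noise between 500 and 1,000 Hz would fold back into the recorded band and could not be removed afterwards.

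Second, and independently of aliasing, the H-reflex typically lies 30 to 40 ms after the stimulus, which is about ten samples. A peak and trough read from so few points will usually miss the true extremes, so the raw amplitude is understated.

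Both terms of the H/M_max ratio come from this signal, M_max rests on few responses, and there are only seven participants. A distortion that differed between baseline and late training could therefore blur or mimic a fall in the H-reflex.

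**Working it through.** The plan gives no figure of its own to reproduce on this point. The documents supply the 3-1,000 Hz band, the 1 kHz rate, the 30-40 ms window, the biphasic shape, 225 responses per session, six sessions per period and seven participants. The wave shape (derivative of a Gaussian), the peak-to-trough separations, the background level and the size of the H-reflex fall are assumptions.

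**1. Frequency limit.** 1,000/2 = 500 Hz. Content at frequency f folds to |f − 1,000 × round(f/1,000)|: 600 Hz appears at 400 Hz and 900 Hz at 100 Hz. The mismatch is exact and needs no assumption.

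**2. Missed peaks.** A biphasic wave filling the 10 ms window has a peak-to-trough separation of about 5 ms. Loss over all sampling phases on a 1 ms grid, without noise:

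| Separation | Mean loss | Worst loss | SD of loss |
|---|---|---|---|
| 5 ms | 1.3% | 3.7% | 1.18% |
| 4 ms | 2.1% | 5.7% | 1.81% |
| 3 ms | 3.6% | 9.6% | 3.18% |

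The loss always lowers the raw amplitude.

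**3. Cancellation.** Let sampling shrink H by a factor a and M_max by a factor b. The outcome is then (aH_late/bM_late) ÷ (aH_base/bM_base) = (H_late/M_late) ÷ (H_base/M_base). Constant factors drop out, even if a and b differ. Only variation in the loss between sessions remains.

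**4. What remains for one participant.** Take CV = SD of loss/(1 − mean loss). At 5 ms this is 0.0118/0.9867 = 0.0120; at 3 ms it is 0.0318/0.9636 = 0.0330.

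- Sampling phase random from trial to trial, H only: CV × √(2/(6 × 225)) = 0.05% at 5 ms and 0.13% at 3 ms.
- Adding M_max as the mean of two responses, whose term is CV × √(2/(6 × 2)): about 0.5% and 1.4%.
- Sampling phase fixed within a session and redrawn between sessions, for both H and M_max: CV × √(2/6) × √2 = about 1.0% and 2.7%. Dividing by √7 for the group mean gives about 0.4% and 1.0%.

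In simulation, 49% to 50% of the fixed-phase contrasts fell below zero, so this noise has no direction. If the sampling phase or latency shifted systematically between the two periods, the ratio could move either way by at most about 4% at 5 ms. Nothing in the documents suggests such a shift.

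**5. Background EMG, aliasing and interpolation.** Assume a 5 ms separation, a true ratio of 0.70, background SD of 5% or 10% of the full H-reflex, and a share of background power above 500 Hz with total power held fixed. Ratio of late to baseline mean amplitude:

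| Background SD | Share above 500 Hz | Raw 1 kHz | Interpolated |
|---|---|---|---|
| 5% | 0% | 0.720 | 0.725 |
| 5% | 10% | 0.719 | 0.725 |
| 10% | 0% | 0.749 | 0.759 |
| 10% | 10% | 0.749 | 0.758 |

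Across shares of 0%, 1%, 5% and 10%, the raw ratio ran from 0.7190 to 0.7196 at the lower background and from 0.7491 to 0.7499 at the higher. Aliasing therefore moved it by less than 0.1 percentage point. All ratios exceed 0.70 because background adds to peak-to-peak amplitude in both periods. Interpolation restores the peaks of the background as well as those of the reflex, so its ratio lies slightly further from 0.70. A second simulation with similar assumptions gave 0.702-0.730 from raw samples and 0.703-0.734 after interpolation, with almost the same trial-level SD.

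**The case for a change.** The best case for acting is that the settings as written cannot both be right without aliasing, that the signal feeds the main outcome, and that the remedy is cheap. On a noise-free wave, interpolation recovers peak-to-peak amplitude to within 0.08%. The authors already processed some data offline: for one participant, "In offline analysis, we used a best decaying exponential fit to obtain the H-reflex estimate". Narrower waves lose more than the 5 ms case, M_max has few responses behind it, and with seven participants avoidable noise is unwelcome.

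Part of this stands. The inconsistency is genuine, no other passage resolves it, and the amount of aliasing is unknown. It is also true that missed peaks lower raw amplitude in one direction only.

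The rest does not lead to a change. The noise-free recovery figure does not carry over to trials recorded on a voluntary background of 10-20% MVC, where interpolation did not improve the ratio. It also cannot undo aliasing. The larger losses need separations narrower than the stated window suggests. M_max was modelled with the H-reflex wave shape although the M-wave window (about 10-25 ms) is longer; at an 8 ms separation the mean loss is only 0.5%. Advice on new recordings has little to act on, because the document describes sessions already completed. A short methods text that does not mention interpolation also does not show that none was used.

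**Conclusion.** No change to the plan is warranted. The stated filter and sampling rate are incompatible, and 1 kHz may be a slip: the same figure is given for ground reaction force, though the documents cannot settle this. If the true rate was 2 kHz or more, only the sentence is wrong. If it was 1 kHz, the missed-peak effect on the baseline versus last-six-sessions contrast is noise of roughly 0.4% to 1.0% on the group mean in the severe fixed-phase case, and less if the sampling phase varies from trial to trial. No material bias towards down-conditioning is shown.

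This rests on an assumed Gaussian-derivative wave with a separation of 3 to 5 ms, a stable acquisition chain across sessions, and an assumed share of at most 10% of background power above 500 Hz. The true share is not in the documents. Confirming the rate, or noting it as a minor measurement limitation, would tidy the report but would not alter the outcome definition, the test or the interpretation.

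### Does the 10.00 dollar payment maximum, which the reward formula can exceed, call for a change to the plan?

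*Combined protocol and SAP*

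**What the plan says.** The FEEDBACK section sets out the payment rule in four parts.

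- **Score.** "The participant's score for each run was cumulative success rate", that is, successes divided by trials, as a percentage.
- **Reward.** The text says that "participants were rewarded in proportion to one's score", using the expression "1.0 + 0.05 * (Scr - 50"), in dollars.
- **Runs.** "each of 24 training sessions consisted of 20 control trials and 3 runs of 75 training trials".
- **Bonus and maximum.** The condition for the bonus is "consecutive success rates that were equal to or higher than 90% for all three runs". Participants who met it received "an extra dollar as bonus, which made the maximum additional compensation amount" 10.00 dollars.

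The section gives no cap on the score or the payment and no floor at zero. It does not say over what period the 10.00 dollars is a maximum. Success is judged against a moving target: "The threshold was updated for each run as the 66th percentile of the H-reflex trials from the previous run".

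**The concern.** The score can run up to 100%, but the stated maximum matches a score of 90%, which is where the bonus begins. A reader who applies the formula at 100% gets more than the maximum. At the other end, a score below 30% gives a negative reward, which makes no sense as a payment.

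This could matter because the study trains participants by operant conditioning and links money to success. If the reward keeps rising above 90%, better control of the reflex earns more. If an unstated cap applies, the reward goes flat. Those are different reinforcement schedules, and someone repeating the study would want to know which was used. A maximum payment should also be stated correctly wherever compensation is described.

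**Working it through.** **Inputs, all from FEEDBACK.** Reward per run R(s) = 1.0 + 0.05 x (s - 50) dollars, with s in percent. Three runs of 75 training trials per session. Bonus of 1.00 dollar if every run has s of at least 90. Stated maximum 10.00 dollars. Reading that maximum as per session is an inference from the three-run bonus.

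**Reproducing the stated figure.** R(90) = 1.0 + 0.05 x 40 = 3.00, and 3 x 3.00 + 1.00 = 10.00. The other readings tried do not give it:

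| Reading, at s = 100 | Dollars |
|---|---|
| Three runs, no bonus | 3 x 3.50 = 10.50 |
| Three runs, one bonus | 3 x 3.50 + 1.00 = 11.50 |
| One score per session, one bonus | 3.50 + 1.00 = 4.50 |
| Three runs, bonus paid for each run | 3 x 4.50 = 13.50 |
| 24 sessions of three runs, one bonus each | 24 x 11.50 = 276.00 |

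**Top of the scale.** R(100) = 1.0 + 0.05 x 50 = 3.50, so the maximum under the rule as written is 11.50. The gap is 11.50 - 10.00 = 1.50 dollars, or 15% of the stated figure.

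**Attainable scores.** With 75 trials, 90% would be 67.5 successes, which cannot occur. The lowest score that earns the bonus is 68/75 = 90.7%, where R = 3.033. Three such runs pay 9.10 + 1.00 = 10.10. So every full session that earns the bonus passes 10.00 unless a cap applied.

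**What a cap would look like.** Limiting each run to 3.00 dollars, or limiting the session total to 10.00, would each make the stated maximum true. The two differ in other cases. Scores of 100%, 100% and 67/75 (R = 2.967) earn no bonus. They pay 3.50 + 3.50 + 2.967 = 9.97 under a session cap and 3.00 + 3.00 + 2.967 = 8.97 under a run cap.

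**Bottom of the scale.** R(30) = 1.0 - 1.0 = 0. At 22/75 (29.3%), R = -0.03. At 0/75, R = -1.50 per run, or -4.50 for three runs. The threshold is the 66th percentile of the previous run, so an unchanged reflex gives about 66% success. If trials are assumed independent, the chance of 22 or fewer successes in 75 is about 1e-10 at a true rate of 66%, and about 0.0002 at 50%.

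**Link to the analysis.** OUTCOME MEASURES defines the outcome from peak-to-peak H-reflex responses normalized to the maximum M-wave and expressed relative to baseline. STATISTICAL ANALYSIS compares baseline with the last six training sessions by a paired t-test. Payment enters neither.

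**The case for a change.** The strongest case for acting is that the three statements cannot all hold for any session that earns the bonus, so the conflict is not confined to a perfect score. Payment tied to success is part of what participants received during training, and the wording about proportion to the score points away from a cap. Replication needs the actual schedule, and a sentence or two would settle it at almost no cost.

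The inconsistency stands, and so does the point that a clear account would help someone repeating the study. Other parts carry less weight. The match of 10.00 to the 90% payout plus bonus fits a cap as well as a slip, so the text does not prove the maximum wrong. A total excess of 24 x 1.50 = 36 dollars per participant needs 100% success in all 24 x 3 = 72 training runs, against a threshold reset before each one; it is a formal bound and not an expected overpayment. The available text does not show what payment figure participants or the ethics board received. FEEDBACK also describes trial-by-trial visual feedback and a running success rate, so money was not the only reinforcement.

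**Conclusion.** The formula, the bonus and the stated maximum disagree by up to 1.50 dollars per session (11.50 against 10.00), on the assumption that the maximum is per session and no cap applied. Either an unstated cap was used or the maximum was miswritten; the document does not say which. The missing floor is a gap on paper only: scores below 30% are remote with this threshold unless the reflex rises sharply between runs, and nothing suggests that anyone was charged.

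No change to the plan follows. The document describes completed recruitment and payments in the past tense, so a cap or floor written in now would alter nothing that participants received; a correction would only record which payment rule was used. The H-reflex outcome, its normalization, the paired t-test and the conclusion drawn from it are the same under every reading. This is a clerical slip in the account of compensation, and correcting it brings no statistical gain.
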